Retention procedures. At baseline, multiple sources of contact information will be recorded for parents and ASUD to prevent attrition. A demographic form will be administered aloud by a research staff member at Brown via Zoom and information will be obtained and stored in hard copy form in locked filing cabinets in the PI's office at Brown University. Contact information will be updated by periodic phone calls and during assessments. Reminders will be made via phone and mail. The PI will hold weekly case review meetings to review no-shows and outreach attempts, and discuss plans to complete contact with missing participants. Compensation for completion of questionnaires and interviews/discussions escalates slightly from \$40 at baseline, 6 and 12 weeks to \$60 at 24 week followThis compensation schedules recognizes the increased effort associated with scheduling a follow-up and providing a urine screen after the teen has been discharged. We have used these retention procedures (e.g., reminder calls, periodic update calls, escalating compensation) with success in current and prior projects.

Randomization. In the randomized pilot trial, parent-adolescent dyads will be randomized to the adapted PW condition or to residential treatment as usual using urn randomization balanced by biological sex (male vs female), race/ethnicity (White, Non- Hispanic vs Non-White, Hispanic), and days of substance use (1-45 vs 45+). Randomization will be done by the research staff using a randomization spreadsheet immediately at the end of the baseline assessment; condition assignments will then be immediately told to the family. Those assigned to the adapted PW condition will be scheduled for their first remote coaching session approximately 4 weeks prior to discharge (described below).

Protecting confidentiality. Steps taken to protect the confidentiality of participants are detailed in **Section D, “Possible Risks and Anticipated Benefits”** in the paragraphs focused on minimizing risk of loss of confidentiality.

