problems (e.g., adolescent substance abuse, curfews, household chores, monitoring of friends, sibling conflict, improving in school, getting up on time, sharing technology, etc.). After selecting a problem, parents view a video clip depicting a family struggling with that problem. Parents are given three possible solutions to the problem to select from, and then receive feedback according to the solution they selected. The feedback is presented in a video enactment of their selected solution and in an explanation of the pros and cons to each choice. This feedback is a critical part of the program, for it points out any errors parents made, explains why ineffective solutions lead to problems, and discusses why effective parenting solutions prevent and solve common family problems. The main parenting behaviors emphasized by each vignette include: 1) problem solving; 2) limit setting; 3) praising; 4) effective communication through I-messages and active listening; 5) supervision and monitoring, and 6) clear communication of teen's behavioral expectations. The program comes with a parent workbook that outlines all of the vignettes included in the program, along with the potential problems and solutions. The workbook also contains a glossary of terms, sample behavior charts, and practice exercises, so that parents can gain additional practice with the skills. The complete PW program takes from 3 to 5 hours to complete depending on the users speed and depth of use. Parents will be asked to create an unidentifiable login and password at enrollment so that they have the option to practice sessions or view any additional sessions at home; parents will then be prompted to generate their own password after the first time they login to the system if they would like. As discussed in the analysis section, we will use these unique logins to monitor parent participants' usage of PW for analyzing parental engagement. The parent coach will encourage parents to complete any sessions at home that they view as relevant to their parenting concerns. Based on parent-adolescent discussion task feedback, we recommend 3-4 PW modules to each family. We encourage parents to tailor the program to their own needs by watching the sessions that apply to them with staff feedback around which sessions may highlight the skills parents are seeking to practice. After discharge, parents will be encouraged via text messages and the online message board to complete additional sessions.

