Individual Coaching Sessions. Individual coaching sessions are designed to individually tailor the PW skills to each parent's presenting concerns. Parents may receive up to 4 sessions by the first follow-up assessment (scheduled 6 weeks post discharge). Based on PI [name]'s consultation with PW developer Consultant [name], we have selected 4 core parenting skills to emphasize in the sessions: I-statements, Contracting, Active Listening, Reframing. The initial session will be 60-75 minutes and will consist of several sections: 1) Rationale for parenting skills, 2) Review of feedback from the baseline in vivo parent-adolescent interaction task in order to cater the computerized parenting program to the families' specific needs 3) Overview of four core parenting skills; 4) Review of PW substance use module, and 5) practice applying the skill to a current problem. Subsequent sessions will be 45-60 minutes and will follow the same basic outline, while introducing the remaining core skills. When parents have questions or introduce problems/complaints about their teen, the coach will first provide validation and then discuss how the parents' problems can be addressed using a skill. Parents will be offered sessions remotely via phone or video-conference technology.

Text-based messaging. Immediately upon enrollment in the PW condition, parents will receive daily text messages for 6 months to reinforce skills from PW, to motivate continued participation in PW, and to encourage participation in the online parent message board (described below). Parents will be able to choose if they want to receive the text messages in English or Spanish. Approximately half of the texts reinforce material taught in PW, along with a link to a video clip enacting a core PW skill. For example, a message might contain a simple reminder statement about a parenting strategy such as limit- setting, monitoring, and communication with a link to a video clip demonstrating this strategy. The second half of all text messages either offer an encouragement for the parent to complete more PW sections or an encouragement to

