We will begin by comparing the DV scores (means of continuous DVs and percentages of categorical DVs) at each assessment. We will conduct separate mixed models predicting each DV by condition, controlling for the following covariates: baseline status on the DV, baseline differences between groups, and any mental health or substance use treatment received over the follow-up period. We will analyze the effect of PW dosage on each DV and calculate partial eta squared (η^2) to estimate the proportion of variance caused by PW. We are underpowered to test mediation, but will examine the effects of PW on our putative mediators (Aim 4), and correlations between change in the mediators and change in the primary outcomes (Aims 2-3), with the goal of finding promising trends to pursue in a larger trial. We will cautiously attempt more sophisticated analyses using hierarchical modeling, a flexible approach to analyzing change that has been frequently used by the PI [37, 90, 91]. Mixed models are ideally suited to address Aims 2-4, by enabling us to compare the conditions at each time point while accounting for the correlation of observations over time. Although convergence is challenged in a small sample, it is feasible. Our primary goal will be to provide measures of association and 95% confidence intervals to reveal the ES of PW on each DV.

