Sample Size, Power, and R01. We chose to recruit 60 subjects for the RCT conservatively estimating that 15-20% may be lost to follow-up, leaving 50 subjects with complete parent-teen data. This number will allow us to make judgments regarding feasibility and acceptability. As noted in Preliminary Studies, ES estimates in prior PW studies have ranged from small to very large; the only ASUD study found small to medium ES, but unlike this application, that study did not offer in-person support or an online parent board. We therefore may find ES in the medium range. Despite issues with ES stability in small samples [124], a small to medium ES paired with high levels of feasibility and acceptability would be an indication that the adapted PW intervention should be tested in a larger trial. Based on the detected ES, post-hoc power analyses will be conducted to determine the number of parents required for a fully powered RCT. For instance, for power of .8, a small ES ($d = .3$) would require a sample of 175 per group, while a medium ES ($d = .5$) would require a much smaller sample of 64 per group. If our results are promising, we will develop a fully powered R01 application in Months 31-36 (see Table 2) to evaluate the adapted PW under ecologically valid conditions. To speed the translation of research findings to practice, our R01 will use a hybrid effectiveness-implementation design to simultaneously test the effectiveness of the intervention and inform the ideal implementation strategy [125].

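### Partial eta squared from parent-chosen PW dosage is to be read as variance caused by PW, but the dosage association is not a causal effect

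*Combined protocol and SAP*

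**What the plan says.** All places are in Section C.2 of the combined protocol and SAP.

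- **Data Analysis Plan, Aims 2-4.** The plan states "We will analyze the effect of PW dosage on each DV and calculate partial eta squared", and the same sentence gives the purpose: "to estimate the proportion of variance caused by PW". It does not define dose. It does not say whether the analysis covers the PW arm only or both arms with treatment as usual set to zero, and it does not label the analysis exploratory.
- **Same paragraph.** Separate mixed models by condition are planned, adjusted for "baseline status on the DV, baseline differences between groups, and any mental health or substance use treatment received over the follow-up period". The stated primary goal is measures of association with 95% confidence intervals. The opening of the Data Analysis Plan commits to intent-to-treat for all 60 parents.
- **Randomization.** "parent-adolescent dyads will be randomized to the adapted PW condition or to residential treatment as usual using urn randomization". Dose is not assigned.
- **Parenting Wisely (PW).** "We encourage parents to tailor the program to their own needs by watching the sessions that apply to them". On logins: "we will use these unique logins to monitor parent participants' usage of PW for analyzing parental engagement".
- **Individual Coaching Sessions.** "Parents may receive up to 4 sessions by the first follow-up assessment".
- **Sample Size, Power, and R01.** A small to medium effect size, together with high feasibility and acceptability, would support a larger trial. Then: "Based on the detected ES, post-hoc power analyses will be conducted". The source analysis is not named.

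**The concern.** How much PW a parent uses is decided after randomisation, largely by the parent. The plan itself treats usage as a measure of engagement. A parent who logs in often and attends coaching may differ from one who does not in motivation, available time or the teen's current state, and each of these can affect the outcome directly. None of the listed covariates measures this. The dosage association therefore mixes any PW effect with the effect of being an engaged parent.

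Time order adds to the problem. Message-board participation is encouraged up to the 24-week assessment, so a dose total taken over the whole study would partly follow the 6- and 12-week outcomes and could be a response to them.

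The chosen index makes this harder to see. Partial eta squared is a squared quantity, so it looks the same whether more use goes with better or with worse outcomes. It is biased upward in small samples. It also has no natural definition for binary outcomes such as the urine screen result or relapse.

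At stake is the causal statement made about PW on each outcome. If the number were also taken as the effect size for planning the next trial, that plan would rest on a non-randomised comparison.

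**Working it through.** **1. The plan's own figures.** The plan gives no value of partial eta squared. Its only effect-size figures are the per-group sizes for a future trial at power 0.80. With two-sided alpha 0.05 (assumed, in line with the 95% intervals), n per group = 2(1.960 + 0.842)²/d².

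- d = 0.3: 2 × 7.85/0.09 = 174.4, so 175 (176 by the exact t calculation). Plan: 175.
- d = 0.5: 2 × 7.85/0.25 = 62.8, so 63 (64 by the exact t calculation). Plan: 64.

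Both reproduce. They are sizes for a two-group contrast.

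**2. Sample available.** 60 × 0.85 = 51 and 60 × 0.80 = 48. The plan uses 50, or 25 per arm if allocation is 1:1 (assumed; the ratio is not stated).

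**3. Chance level.** Partial eta squared = SS(term)/[SS(term) + SS(error)]. For one term with 1 degree of freedom and no true association, and no other covariate, its mean is 1/(n − 1).

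- Dose within the PW arm, n = 25: 1/24 = 0.042.
- Condition contrast, n = 50: 1/49 = 0.020.

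The 0.020 is a property of the index at this sample size. It applies to the randomised contrast as much as to any other single term.

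**4. Adding confounding, with the PW effect set to exactly zero.** A latent engagement variable is correlated with outcome (b) and with the propensity to take up dose (a). Dose is 0 to 4 sessions in the PW arm and 0 in controls, with 25 per arm. The documents give neither correlation, so a range is shown with b = 0.3. Figures are simulation means, which repeat runs move by a few thousandths.

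| a (engagement with dose) | b (engagement with outcome) | Dose within PW arm: mean eta squared | p < .05 | Dose in a model with arm, n = 50: mean partial eta squared |
|---|---|---|---|---|
| 0 | 0 | 0.042 | 5% | 0.021 |
| 0.3 | 0.3 | 0.049 | 8% | 0.025 |
| 0.5 | 0.3 | 0.058 | 10% | 0.029 |
| 0.7 | 0.3 | 0.078 | 16% | 0.040 |
| 1.0 | 0.3 | 0.116 | 29% | 0.060 |

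The randomised condition contrast stays at about 0.02.

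The pattern follows from the implied squared dose-outcome correlation, (ab)². This is 0.15² = 0.0225 at a = 0.5 and 0.30² = 0.09 at a = 1.0. It comes on top of the chance level and is slightly reduced because dose is a whole number limited to 0 to 4.

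**5. A separate run with baseline adjustment.** Here the baseline value of the outcome is a covariate (assumed correlation 0.5 with follow-up), with 6,000 replicates and a = b.

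- a = b = 0.3: mean 0.050 within the PW arm, against 0.044 by chance.
- a = b = 0.5: mean 0.093 within the PW arm; condition contrast 0.021.
- a = b = 0.5 in very large samples: dosage 0.059, condition 0.000. More patients remove the small-sample bias but not the confounding.

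**6. Dependence on the unstated model.** Over a = b from 0 to 0.7, the mean at 25 per arm runs from 0.021 to 0.049 if both arms are pooled without a condition term, and from 0.022 to 0.123 with one. Within the PW arm it runs from 0.044 to 0.239.

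**The case against.** The strongest reply is that this is one supporting analysis within secondary aims of a pilot. The plan commits to intent-to-treat, fits models by condition, and makes effect sizes with 95% confidence intervals its primary goal. The sample-size section works in d and in numbers per group, which is the language of a two-group contrast and mentions neither dosage nor partial eta squared. It also warns that effect sizes are unstable in small samples. All of this stands, and it limits how much is at risk.

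Four stronger readings are tempting, and the documents do not support them.

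- **That the dosage index feeds the go signal and the sizing of the next trial.** A reader might infer this, because partial eta squared is the only effect-size statistic the Aims 2-4 text names. The sample-size section does not say so, and its per-group d figures point to the condition contrast. What stands is that the source of the effect size is not named.
- **That the analysis must overstate PW.** Parents of teens who are doing worse may use PW more, so the confounding need not favour PW. The plan also begins with means and percentages at each assessment, so direction will be visible there. The upward bias is in the size of an unsigned index.
- **That the bias is large whatever one assumes.** The value near 0.12 needs dose to be almost a pure readout of engagement. At 0.3 for both correlations the excess over chance is small (0.049 against 0.042).
- **That the dose term can be turned into an equivalent d.** The usual conversion is for two equal groups and does not carry over to a graded dose term in a model that also contains arm.

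One could also attach partial eta squared to the condition model. The sentence as written joins it to dosage, so this reading would need to be stated.

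**Conclusion.** The point holds as one of interpretation and should be fixed. Followed as written, the plan reports a non-randomised association as variance caused by PW. That dose is not randomised and no listed covariate addresses engagement follows from the text and needs no assumption.

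The size does rest on assumptions. With no PW effect and 25 per arm, mean eta squared within the PW arm is about 0.04 by chance and about 0.06 to 0.12 for an engagement-outcome correlation of 0.3 and an engagement-dose correlation of 0.5 to 1.0. The condition contrast stays at about 0.02. These figures also assume 1:1 allocation, 50 completers, a dose of 0 to 4 sessions and an analysis confined to the PW arm; pooling both arms without a condition term gives lower values.

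The trial's effect estimate as a whole is not compromised, because the randomised comparison is already planned.

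**What to change.** - Delete the clause "to estimate the proportion of variance caused by PW".
- State that the effect of PW, and any effect size used for the go signal or for sizing the R01 trial, comes from the randomised condition contrast: a standardised mean difference, or an odds ratio for binary outcomes, with its 95% confidence interval.
- Label the dosage analysis exploratory and associational, confine it to the PW arm, define dose and the period over which it is counted, and report the direction of the association.
- Do not replace it with an instrumental-variable estimate for attending a minimum number of coaching sessions. Parents in the PW arm also receive daily texts, the message board and the online modules whatever their attendance, so assignment does not act through sessions alone.

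Cost: wording in the analysis plan only, with no new data and no change to the sample size. The downside is that the reported effect sizes may be smaller.

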By using the GAIN at follow-ups, we will capture continuous data on the teen's use and high-risk behaviors following discharge. We will also include measures of parental communication and monitoring (Aim 4), as these outcomes are not included in the GAIN and parenting practices are a key factor associated with ASUD. PI [name] is a certified GAIN trainer and has experience analyzing GAIN data. Specific scales that we will analyze to address Aims 2 and 3 are described below.

Demographics. The GAIN Background section collects routine socio-demographic variables including age, sex, ethnicity, race, and grade in school. Items in other GAIN sections indicate the teen's history of substance use or mental health treatment utilization, data that will be used to control for additional treatment received.

Substance Use. The following GAIN items/scales and biological markers will address Aim 2 (substance outcomes).

Days of Use (Past 90 Days). A series of GAIN items evaluate days of substance use over the past 90 days. These items have shown excellent comparability to the well-validated Timeline Follow-Back Interview (TLFB). Like the TLFB, the GAIN assesses days of alcohol and drug use using a calendar with temporal cues (e.g., holidays, special events) to facilitate recall. We will analyze three variables, separately for alcohol, marijuana, and other drugs: total number of use days, total days abstinent, and latency to first use.

Substance Frequency Scale (SFS). The SFS scale averages the percent of days in the past 90 during which there was use of alcohol, marijuana, or heavy drugs; use to intoxication; and failure to perform activities due to use. This scale has good reliability ($\alpha = .85$) and predicts substance-related problems as well or better than biometric (e.g., urine) markers of use.

Biological markers. Biological markers will **only be used at the follow-up assessments (6, 12, and 24 weeks)**, since adolescents are not expected to have access to substances at the time of the baseline assessment (likely to be at least 1-2 days after admission). 8-panel urine screens that detect the presence of marijuana, cocaine, amphetamines, methamphetamines, MDMA, opiates, oxycodone, and benzodiazepines mailed to each family and administered to the teens by the parents will be used to provide a biological indicator of abstinence. Teens who present as acutely intoxicated based on researcher observations, parent-report, or adolescent-report will be rescheduled.

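### The fully powered trial is to be sized on the pilot's detected effect size, with the outcome, time point and metric left open; if the true effect is small, that sizing falls short of .8 power on average

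*Combined protocol and SAP*

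**What the plan says.** The section Sample Size, Power, and R01 randomises 60 dyads and allows for 15–20% loss, "leaving 50 subjects with complete parent-teen data". It adds the caveat "Despite issues with ES stability in small samples", then says that "a small to medium ES paired with high levels of feasibility and acceptability would be an indication" that a larger trial is warranted. No numerical cut-off is given. The sizing rule follows: "Based on the detected ES, post-hoc power analyses will be conducted to determine the number of parents required for a fully powered RCT". The worked examples, starting "For instance, for power of .8, a small ES", give 175 per group at d = .3 and 64 per group at d = .5.

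The Data Analysis Plan (Aims 2-4) fits a separate mixed model to each dependent variable, with the baseline value as a covariate. It states "Our primary goal will be to provide measures of association and 95% confidence intervals to reveal the ES of PW on each DV". Its only named effect-size statistic comes in the dosage sentence: "We will analyze the effect of PW dosage on each DV and calculate partial eta squared".

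**The concern.** The rule turns one noisy estimate into the size of the next trial, straight after conceding that such estimates are unstable. The same estimate also has to look promising before anyone proceeds, so the estimates that reach the sizing step tend to be too large. Required size varies as 1/d², so overestimates cut the trial sharply.

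The rule also cannot be applied as written without further choices. Aim 2 alone offers days-of-use variables for three substance classes, the SFS and urine screens, and there are three follow-up visits. The examples are in d, the analysis section names partial eta squared, and no standardising SD is stated. Different choices give different trial sizes.

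The Application section gives informing the design of a fully powered trial as one of two reasons for adding the second site. The sizing step therefore serves a declared purpose.

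**Working it through.** **Inputs.** From the plan: 60 randomised, about 50 complete, power .8 (given only as an illustration). Assumed: 1:1 allocation, so 25 per arm (30 if nobody is lost); two-sided .05; the go rules below; a baseline-to-follow-up correlation r of .5 where adjustment is modelled.

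**1. The plan's own figures.** n per group = 2(1.96 + 0.8416)²/d² = 15.70/d².
- d = .3: 174.4, rounded up to 175 (176 by the t calculation).
- d = .5: 62.8, rounded up to 63 (64 by the t calculation).

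The plan's 175 and 64 are correct. One-sided .05 would give 138 and 50, so two-sided .05 is the natural reading.

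**2. Precision of the pilot.** SE(d) ≈ √(2/n + d²/(4n)). With n = 25 and an observed d of .5, SE = √(.080 + .0025) = .287, and the 95% interval is about −.06 to 1.06. The upper limit implies 15.70/1.06² ≈ 14 per arm. The lower limit implies no finite size.

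**3. One unlucky case.** Suppose the pilot shows d = .5 and the next trial takes 64 per group. If the true d is .3, power is Φ(.3 × √(64/2) − 1.96) = Φ(−.26) ≈ .40. With a true d of .3, a pilot of 25 per arm shows .5 or more about 25% of the time.

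**4. Average over pilots.** Simulate the pilot d with error variance multiplied by (1 − r²). Size the next trial as 15.70(1 − r²)/d_obs², rounded up. Compute its power at the true d with the same adjusted variance, and average over pilots that go forward. Setting r = 0 gives the unadjusted case. Ranges span 25 and 30 per arm, with the effect standardised on the total SD. At true d = .3:

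| Go rule (assumed) | Adjusted throughout, r = .5 | Unadjusted |
|---|---|---|
| Any positive estimate | 67–69% | 65–67% |
| At least .2 | 56–58% | 53–55% |
| Between .2 and .5 | 70% | 70% |

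Standardising on the residual SD instead leaves all three adjusted figures below 80%. Unadjusted, with a floor of .2 and a true d of .3, the mean detected d is .47 (25 per arm) and the median size is 83–90 per arm against 175 needed. The 10th to 90th percentiles run from about 29 to 264.

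**5. Larger effects (unadjusted).** At true d = .5: 66–68% (floor .3), 70–71% (floor .2), 73–74% (any positive), 94% (band .2–.5). At d = .8: 76–78% for the three open-ended rules.

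**6. Where the shortfall disappears at d = .3.** If the next trial is sized without baseline adjustment but analysed with it at r = .7, mean power is 80–82% (floor .2), 85–87% (any positive) and 90% (band). At r = .5 the same mismatch gives 55–67% across floors of .2 and .3.

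**7. Metric.** At r = .5, a d of .50 on the total SD is .50/√.75 = .58 on the residual SD. Entered in the formula of step 1, these give 63 and 48 per group.

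**8. Visit, for 90-day-recall GAIN measures.** "The SFS scale averages the percent of days in the past 90 during which there was use". If that window is unchanged at follow-up, the 6-week visit covers 6 × 7 = 42 post-discharge and 48 earlier days, and the 12-week visit 84 and 6. At 24 weeks (168 days) all 90 days fall after discharge.

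**The case against.** The strongest reply is that this is a pilot whose first aim is feasibility, that the plan admits effect-size instability and makes confidence intervals its main deliverable, and that a later grant application with a different, hybrid design can revisit the sizing. Much of this stands, and it lowers the priority. It does not change the rule, which names the detected effect alone and gives the interval no part in the sizing.

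Several stronger readings are tempting but unsupported:

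- **No effect-size metric is named.** Not so: d appears in the examples and partial eta squared in the dosage sentence. What is missing is which one the detected effect will be, and on what SD.
- **A single visit must be chosen.** The mixed models cover all follow-ups, so a condition effect pooled over follow-up is equally legitimate. The gap is that the choice is unstated. The analysis section treats Aims 2-3 as the main outcomes and Aim 4 as mediators, which narrows the field without selecting a variable.
- **The effect measures something different at each visit for every outcome.** The window problem applies to 90-day-recall GAIN measures only. It does not reach the urine screens, the FAsTask, or the PMQ and PACS as described.
- **The next trial will be underpowered whatever the truth.** Steps 5 and 6 contradict this.
- **The pilot's own size or conduct is at fault.** Nothing here bears on either.

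**Conclusion.** The point holds in a limited form. The follow-on trial is sized on a point estimate from about 50 completers, with outcome, time point and metric unresolved and the interval unused. At a true d of .3, mean power is roughly 56–70% with baseline adjustment throughout and 53–70% without, under the three tabulated go rules, against the .8 in the plan's example. A small effect is plausible on the plan's own account, which reports small-to-medium effects in the one earlier study in this population.

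The shortfall is secure only for small effects. At d = .5 the unadjusted result runs from 66% to 94% depending on the go rule, and at d = .8 it is slight for open-ended rules. Even at d = .3 it can vanish when strong adjustment is used in the analysis but ignored in the sizing. The go thresholds, correlations, allocation ratio and two-sided .05 are assumptions. The harm falls on the next trial, not on this pilot's N, conduct or feasibility aim. This is a cheap improvement of lower priority.

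**What to change.** Replace the sizing sentence in Sample Size, Power, and R01 with:

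> The fully powered RCT will be sized for .8 power at a minimum worthwhile effect on [one DV, at one visit or pooled over follow-up, with the ES metric and standardising SD stated], justified in advance; the pilot will supply the SD, baseline-to-follow-up correlation, retention and recruitment; the pilot 95% CI will be used only to check that this effect is not ruled out.

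The investigators must justify the effect; the plan's d = .3 and d = .5 are illustrations. If they choose a 90-day-recall GAIN measure, the text should note that only the 24-week window lies wholly after discharge. The Application section looks back on the end of the study, so analysis may have begun. If it has, the text should say that the choice was made afterwards and not present it as prespecified.

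Cost: wording only, with no change to pilot enrolment or data collection. There are two downsides. The planned follow-on trial will probably be larger. The interval check is also weak at this pilot size: with a true d of 0, it rules out an illustrative d of .3 in only 18–21% of pilots unadjusted and about 23–27% adjusted at r = .5.
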